## 1. SYNOPSIS

CLINICAL STUDY SYNOPSIS: AXS-05-AD-301	
Product Name/ Number	AXS-05 (bupropion hydrochloride and dextromethorphan hydrobromide monohydrate)
Protocol Number	AXS-05-AD-301
Protocol Title	A Randomized, Double-blind, Placebo-controlled Trial to Assess the Efficacy and Safety of AXS-05 for the Treatment of Agitation in Subjects with Dementia of the Alzheimer's Type
Indication	Treatment of agitation associated with dementia of the Alzheimer's type
Development Phase	2/3
Objective	The primary objective of the study is to evaluate the efficacy and safety of AXS-05 compared to placebo and bupropion sustained release (SR) for the treatment of agitation in subjects with dementia of the Alzheimer's type.
Study Design	
This trial is a multi-center, randomized, double-blind, double-dummy, placebo-controlled study, consisting of 5 weeks of treatment. Eligible subjects for this study must have a diagnosis of probable Alzheimer's disease (AD) and must have clinically meaningful agitation secondary to AD. Following screening procedures for assessment of inclusion and exclusion criteria, eligible subjects will be randomized in a 1:1:1 ratio to be treated with AXS-05, bupropion sustained release (SR), or placebo. As part of protocol amendment 2, randomization to the bupropion arm was discontinued.
 
The primary efficacy endpoint is the change from baseline to Week 5 in the Cohen-Mansfield Agitation Inventory (CMAI) total score.
  
Screening Period
 
Prior to randomization, all potential subjects will enter an up to 4-week screening period (Screening) to determine eligibility. In order to be eligible, subjects must have a diagnosis of probable AD according to the 2011 National Institute on Aging-Alzheimer Association (NIA-AA) criteria, and a diagnosis of agitation according to the International Psychogeriatric Association (IPA) provisional definition of agitation.
 
Eligible subjects must have symptoms of agitation (intermittently or constantly) at the time of screening and for at least 2 weeks prior to randomization, and the agitation symptoms must be severe enough such that they interfere with daily routine and for which a prescription medication is deemed indicated, in the opinion of the current treating physician.
  
Treatment Period
 
Randomization
 
Eligible subjects who successfully complete Screening will be randomly assigned at the baseline visit (Baseline) to receive AXS-05, bupropion SR, or placebo, orally, twice daily, in a 1:1:1 ratio, for 5 consecutive weeks. As part of protocol amendment 2, randomization to the bupropion arm was discontinued.
 
The randomization schedule will be computer-generated using a permuted block algorithm that will randomly allocate the study drug to randomization numbers. The randomization will be stratified by region (US or Ex-US) and by antipsychotic use (yes or no).

Treatments

Doses will be titrated as follows:

- AXS-05 group: 105 mg bupropion/45 mg dextromethorphan BID
- Bupropion group: 105 mg bupropion BID
- Placebo group: placebo BID

All doses will be taken at least 8 hours apart, orally on an empty stomach (at least 2 hours pre- or post-prandial) with water.

All study medication including AXS-05 tablets, bupropion SR tablets, and placebo tablets are of identical appearance in order to maintain the integrity of the blind.

Rescue Medication

Patients will be allowed to receive oral lorazepam as rescue medication for the short-term treatment of symptoms of agitation if deemed necessary by the investigator. Lorazepam (0.5 mg tablets) will be administered in a total dose up to 1.5 mg/day and not to exceed 3 days in a 7-day period. Caregivers must record concomitant use of lorazepam in the Caregiver Diary.

Assessments and Visits

[figure not shown]
Study visits will occur at Screening (Visit 1), Baseline (Day 1, Visit 2), and on Days 8, 15, 22, 36 (Visits 3-6). Study procedures will be performed, and questionnaires for the evaluation of efficacy parameters will be administered during study visits. A safety follow-up phone call (Visit 7) will be conducted 1 week after the last dose of study drug (Day 43).

Caregivers will be provided with a Caregiver Diary at each study visit and will be instructed to record daily 1) any agitated or abnormal behaviors if they occur, including the number of times they occurred that day, 2) the number of tablets of study medication taken and the time of administration, 3) the dose of rescue medication administered and the time of administration if administered, and 4) any changes in the subject's physical status or mental status such as, dizziness, unusual weakness, falls, confusion or obvious worsening of memory problems, worsening agitation, any loss of consciousness, or seizures. Diaries will be reviewed during study visits.

A blood sample for cytochrome P450 2D6 (CYP2D6) genotyping will be collected at the Baseline visit. Blood samples for measurement of study drug concentrations will be collected on Day 15 (Visit 4) and on Day 36 (Visit 6).

The study design is summarized in the Figure below.

**AXS-05-AD-301 Study Design**

Planned Number of Subjects	Approximately 435 subjects (145 per arm) will be randomized to achieve approximately 300 completed subjects. As part of protocol amendment 2 , randomization to the bupropion arm was discontinued.
Study Centers	Up to approximately 60 study centers in the U.S., Canada, and Australia.
Diagnosis and Subject Selection Criteria -Inclusion Criteria -Exclusion Criteria	Inclusion Criteria: 

1. Male or female outpatients, 65 to 90 years of age, inclusive.

2. Diagnosis of probable Alzheimer’s disease (AD) based on the 2011 National Institute on Aging-Alzheimer Association (NIA-AA) criteria.

3. Clinically significant agitation, at the time of screening and for at least 2 weeks prior to randomization, that interferes with daily routine activities and for which a prescription medication is deemed indicated, in the opinion of the investigator.

4. The diagnosis of agitation must meet the International Psychogeriatric Association (IPA) provisional definition of agitation, as evidenced by each of the following:

A. The patient exhibits at least one of the following behaviors that are associated with observed or inferred evidence of emotional distress (e.g. rapid changes in mood, irritability, outbursts), and the behavior has been persistent or frequently recurrent for at least 2 weeks and represents a change from the patient’s usual behavior:

a) Physical aggression (e.g. grabbing, shoving, pushing, resisting, hitting others, kicking objects or people, scratching, biting, throwing objects, hitting self, slamming doors, tearing things, and destroying property)

b) Verbal aggression (e.g. yelling, speaking in an excessively loud voice, using profanity, screaming, shouting)

c) Excessive motor activity (examples include: pacing, rocking, gesturing, pointing fingers, restlessness, performing repetitious mannerisms)

B. Behaviors are severe enough to produce excess disability, which in the clinician’s opinion is beyond that due to cognitive impairment and including at least one of the following:

a) Significant impairment in interpersonal relationships.

b) Significant impairment in other aspects of social functioning.

c) Significant impairment in ability to perform or participate in daily living activities.

C. The agitation is not attributable solely to another psychiatric disorder, suboptimal care conditions, medical condition, or the physiological effects of a substance.

 
■ [REDACTED]
 
■ [REDACTED]
 
7. Caregiver must be:

a) A family member who has been providing care to the patient for at least 3 months prior to Screening.

b) Knowledgeable of the patient, and reliable in providing care to the patient.

c) In regular contact with the patient and spend a minimum of 16 hours per week (a minimum of 4 hours on 4 separate days) with the patient.

d) Capable, in the opinion of the investigator, of providing an adequate rating of the patient’s condition.

 
8. Caregiver must also:

a) Be able and willing to communicate with site personnel and to comply with all required study procedures including not administering any prohibited medications during the course of the study, and to oversee the patient’s compliance with the study treatment.


	

b) Agree to accompany the patient to all site visits, be available by telephone at designated times, and be able and willing to observe for possible adverse events and to report on the patient's status.

c) Fully understand the length of the trial.

d) Agree to undergo training in recognizing agitation symptoms and in rating of the scales used in the study.

 
9. Caregiver signed and received a copy of a caregiver's ICF after the nature and risks of study participation had been fully explained.
 
10. Patients capable of signing consent (according to the investigator), or their authorized representatives, signing and receiving a copy of the patient's ICF after the nature and risks of study participation have been fully explained to them.
 
11. Patients who are capable of providing assent but not capable of signing the ICF, according to the investigator, should provide assent for study participation.
 

a) Patients who sign the ICF are not required to provide a separate assent.

b) Patients who are not capable of providing assent are still allowed to participate provided the patient's authorized representative agrees to participation. Investigators must document the reasons for any patient who is unable to provide assent and maintain this documentation with the consent/assent documents.

 
12. The patient has stable cardiac, pulmonary, hepatic, and renal function.
 
13. Patients currently receiving a drug for the treatment of AD (e.g., donepezil, rivastigmine, galantamine, memantine) are eligible provided they have been on a stable dose of these medications for at least 2 months prior to randomization.
 
14. Patients currently taking allowed medications for the treatment of agitation secondary to AD (e.g., antipsychotics, buspirone) are eligible provided they have been on a stable dose for at least 4 weeks prior to randomization. Patients who have recently discontinued these medications must be off them for at least 4 weeks prior to randomization. Antipsychotics which are primarily metabolized by CYP2D6 are exclusionary (see permitted and prohibited medications section).
 
15. Concomitant use of low dose trazodone (up to 50 mg/day), melatonin, eszopiclone, zolpidem, zopiclone or zaleplon for nighttime management of insomnia, provided the dose and regimen have been stable for at least 1 month prior to randomization and remain stable throughout the study, is allowed. Contact the medical monitor regarding the use of other sleep aids.
 

 
Exclusion Criteria:
 

1. Caregiver is unwilling or unable, in the opinion of the investigator, to comply with study instructions.

2. Patient has dementia predominantly of non-Alzheimer's type (e.g., vascular dementia, frontotemporal dementia, Parkinson's disease, substance-induced dementia).

3. Patient is hospitalized in a mental health facility (e.g., psychiatric hospital or ward), or living alone.

4. Patient has symptoms of agitation that are not secondary to AD (e.g., pain, other psychiatric disorder or delirium due to a metabolic disorder, systemic infection or substance-induced).

5. History or current clinical symptoms of schizophrenia, schizoaffective disorder, or bipolar disorder, as defined in the Diagnostic and Statistical Manual of Mental Disorders, 5th Edition (DSM-5).

6. History of alcohol or substance use disorder (other than nicotine or caffeine) within 1 year

--	--

	
of randomization.
 

7. Use of serotonergic medications, such as selective serotonin reuptake inhibitors (SSRIs) and serotonin norepinephrine reuptake inhibitors (SNRIs) are prohibited to avoid the risk of serotonin syndrome. These products are exclusionary if used within 2 weeks, or 5 half-lives, whichever is longer, of randomization.

8. Current use, or use within 14 days before study drug dosing, of monoamine oxidase inhibitors (MAOIs), linezolid, or intravenous methylene blue.

9. History of seizure disorder, anorexia nervosa or bulimia; undergoing abrupt discontinuation of alcohol, benzodiazepines, barbiturates and antiepileptic drugs; or any other condition that increases the risk of seizure such as stroke, significant head injury, tumor or infection of the central nervous system, arteriovenous malformation, neuroleptic malignant syndrome/serotonin syndrome, or clinically significant, as deemed by the investigator, metabolic disorders (e.g., clinically significant hypoglycemia, hyponatremia, severe hepatic impairment, and hypoxia).

10. Any concurrent medical condition that might interfere with the conduct of the study, confounds the interpretation of study results, or endangers the patient's well-being. This includes a history of malignancy within the last two years (except skin basal-cell carcinoma or untreated prostate cancer), or any significant hematologic, endocrine/metabolic (e.g. poorly controlled diabetes), cardiovascular (e.g. poorly controlled hypertension, unstable ischemic cardiac disease, dilated cardiomyopathy, or unstable valvular heart disease), unstable or progressive pulmonary, renal, hepatic, gastrointestinal or neurologic, or other chronic disease. Certain other non-metastatic cancer may be allowed. Each case to be evaluated individually with medical monitor.

11. Hypertension defined as resting, sitting systolic blood pressure (BP) <math>\geq 150</math> mm Hg or diastolic BP <math>\geq 95</math> mm Hg. Patients with systolic BP <math>> 134</math> mm Hg or diastolic BP <math>> 85</math> mm Hg should be receiving adequate treatment for hypertension. Blood pressure values may be confirmed by serial assessments (at least 30 minutes apart), if needed.

12. Gastric bypass or any condition that would be expected to affect drug absorption (lap band procedures are acceptable if there is no problem with absorption).

13. Narrow-angle glaucoma without a patent iridectomy.

14. Known human immunodeficiency virus (HIV) infection.

15. Known history of hepatitis B or C infection.

16. Screening liver enzyme test (e.g., bilirubin, aspartate aminotransferase and/or alanine aminotransferase) results <math>> 2.0 \times</math> ULN.

17. Any clinically significant abnormality on the screening laboratory tests, as assessed by the study investigator and/or the medical monitor.

18. History of allergy or hypersensitivity to bupropion, dextromethorphan, opiate drugs (e.g. codeine, etc.), or any other ingredient in the study medication.

19. History of allergy to benzodiazepines (e.g., lorazepam).

20. History of intolerance to bupropion or dextromethorphan.

21. Patients who have received dextromethorphan co-administered with quinidine (e.g. Nuedexta®) and did not respond to treatment.

22. Patients who have been taking disallowed concomitant medications within 2 weeks or 5 half-lives, whichever is longer, prior to Baseline.

23. Patients currently being treated, or who have been treated with any investigational product (drug or device) within 30 days or 5 half-lives, whichever is longer, of Baseline.

24. Patients determined to have a high imminent risk of falls during the study based on a clinical

--	---

	
evaluation by the investigator.
 
25. Patients with history of postural syncope, or any history of unexplained syncope (evaluated on a case by case basis) within 12 months of Baseline.
 
26. Patient must not show current and significant symptoms of a major depressive disorder or clinically significant risk of suicide or harm to self or others.

Test Product, Dosage, and Mode of Administration
	
[REDACTED]
 
Treatment A (target dose): AXS-05 (105 mg bupropion, 45 mg dextromethorphan) tablet, oral

Reference Therapies, Dosage, and Mode of Administration
	
Treatment B: Bupropion SR (105 mg) matching tablet, oral
 
Treatment C: Placebo matching tablet, oral

Treatment Regimen
	
[REDACTED]
 
 
• AXS-05 group: 105 mg bupropion/45 mg dextromethorphan BID
 
• Bupropion group: 105 mg bupropion BID
 
• Placebo group: placebo BID
 
 
All doses will be taken at least 8 hours apart, orally on an empty stomach (at least 2 hours pre- or post-prandial) with water.

Study Duration
	
Up to 10 weeks: up to 4 weeks Screening, followed by 5 weeks of treatment, followed by a 1-week follow-up visit.

Criteria for Evaluation
	
Primary Outcome Measure:        Cohen-Mansfield Agitation Inventory (CMAI)
 
Primary Endpoint:
 
 
▪ CMAI total score, change from Baseline to Week 5
 
 
Key Secondary Endpoints:
 
 
▪ Modified Alzheimer’s Disease Cooperative Study-Clinical Global Impression of Change for Agitation (mADCS-CGIC Agitation)
 
 
■ [REDACTED]
 
Secondary Endpoints:
 
[REDACTED]

	
Safety Measures	

▪ Adverse Event (AE) recording

▪ Adverse Dropouts (ADOs)

▪ Incidence of Treatment Emergent Adverse Events (TEAEs)

▪ Clinical laboratory test results

▪ Vital sign measurements

▪ ECG findings

▪ Physical examination findings

▪ Columbia – Suicide Severity Rating Scale (C-SSRS)


Statistical Methods
	
Analysis Populations:
 
The following analysis populations are planned for this study:
 
 
▪ Modified Intent-to-Treat (mITT) Population—the mITT will be the primary efficacy analysis population and will consist of all subjects who are randomized, subsequently take at least 1 dose of the study drug, and have at least 1 post-Baseline efficacy assessment
 
▪ Intent-to-Treat Population—the ITT will include all subjects who are randomized
 
▪ Safety Population—the Safety Population will be the primary safety analysis population and will include all subjects who receive at least 1 dose of the study drug
 
 
Primary Efficacy Analysis:
 
The primary endpoint will be the change from Baseline (Day 1) to Week 5 in the CMAI total score. The primary comparison will be AXS-05 versus placebo.
 
The changes from Baseline in the CMAI total score will be analyzed using a Mixed Model with Repeated Measures (MMRM). This model will include treatment, week, and treatment-by-week interaction as factors, Baseline value as a covariate, and subject as a random effect. Treatment effects and the differences between treatments will be estimated using the least-square mean estimates and will be reported together with the 2-sided 95% confidence interval of the treatment difference. The null hypothesis of no treatment difference will be tested at a two-sided significance level of 0.05.
 
Safety Analysis:
 
Adverse events will be coded by system organ class (SOC) and preferred term using the Medical Dictionary for Regulatory Activities (MedDRA) reporting system. TEAEs are those that occur following the start of treatment with study drug through follow up (7 days after the last dose), and SAEs that occur from the start of treatment with study drug through 30 days after the last dose. The number and percentage of subjects with TEAEs will be displayed for each treatment group by SOC and preferred term. Additionally, TEAEs will be tabulated for each treatment group by severity and by relationship to the study drug. A listing of SAEs will be provided if applicable.
 
Descriptive summaries will be calculated, and data listings provided for hematologic, biochemical, and urinalysis laboratory parameters, and vital signs measurements, as appropriate.


Sample Size Determination
	
Approximately 300 completed subjects (100 per treatment group) will provide 90% to detect a treatment difference for the primary efficacy variable (change from baseline in CMAI total score at Week 5) at a two-sided significance level of 0.05. In the sample size calculation, it was assumed the effect size was 0.46. Approximately 435 subjects (145 subjects each in the AXS-05, bupropion SR, and placebo arms) will be randomized to achieve approximately 300 completed subjects, assuming an approximately 30% drop-out rate. As part of protocol amendment 2, randomization to the bupropion arm was discontinued.

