**Schedule of Assessments**

Visit	Screening Visit 1	Baseline Visit 2	Visit 3	Visit 4	Visit 5	Visit 6 / ET a	Follow-up b Visit 7
Study Day	-28 to -1	1	8 (±3)	15 (±3)	22 (±3)	36 (±3)	43 (±3)
End of Week	Weeks -4 to -1		Week 1	Week 2	Week 3	Week 5	Week 6
Informed consent	X						
Inclusion/exclusion criteria	X	X					
Medical history and demographics	X						
Physical examination c	X					X	
Vital signs d	X	X e	X	X	X	X	
Electrocardiogram	X					X	
Review previous and concomitant medications	X	X	X	X	X	X	X
Height and weight	X					X	
Clinical laboratory tests f	X					X	
Columbia Suicide Severity Rating Scale (C-SSRS)	X	X	X	X	X	X	
Randomization		X					
Cohen-Mansfield Agitation Inventory (CMAI)		X	X	X	X	X	
Modified Alzheimer's Disease Cooperative Study-Clinical Global Impression of Change for Agitation (mADCS-CGIC)		X				X	
Administer first dose of study medication in clinic		X h					
Administer last dose of study medication in clinic						X	
Review of adverse events		X i	X	X	X	X	X
Blood sample for drug concentration				X		X j	
Blood sample for CYP2D6 genotyping		X					
Caregiver to Complete Daily Caregiver Diary g		X	X	X	X	X	
Review and return study medication and Caregiver Diary			X	X	X	X	
Dispense study medication		X	X	X			

- a Early Termination (ET) visit for subjects who withdraw prior to study completion, the Follow-up Visit will occur 1 week after ET.
- b Follow up visit may be conducted by phone. If the patient reports AEs that require follow-up an in-clinic visit should be performed.
- c A complete physical examination (excluding breast and genitourinary examination) will be performed at Screening and a brief physical examination will be performed at Week 5 or at Early Termination.
- d Vital signs, including seated and orthostatic blood pressure and pulse, respiratory rate, and oral temperature, will be measured.
- e On Day 1, vital signs should be collected pre-dose and at least 1 hour following the dose.
- f Clinical laboratory tests will include hematology, serum chemistry, and urinalysis.
- g A Caregiver Diary will be used to record the number of tablets of study medication and rescue medication (lorazepam) administered and the time of administration, adverse events, and subject behaviors. Study personnel will train caregivers how to complete the diary, retraining to occur as needed.

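### The synopsis gives a random subject effect as the primary model's only within-subject term; fitted as written, the Week 5 standard error is right only under restrictive assumptions

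*Combined protocol and SAP*

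**What the plan says.** The Primary Efficacy Analysis paragraph of the synopsis (Statistical Methods) sets the target: "The primary endpoint will be the change from Baseline (Day 1) to Week 5 in the CMAI total score". AXS-05 against placebo is the primary comparison. The method is named as a mixed model with repeated measures, and its terms are listed: "This model will include treatment, week, and treatment-by-week interaction as factors, Baseline value as a covariate, and subject as a random effect". The least-squares mean difference from this model "will be reported together with the 2-sided 95% confidence interval of the treatment difference", and the test is stated as: "The null hypothesis of no treatment difference will be tested at a two-sided significance level of 0.05".

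Under Assessments and Visits, post-baseline visits fall at the points given as "and on Days 8, 15, 22, 36 (Visits 3-6"). The Schedule of Assessments marks CMAI at each of them. Its last treatment visit, Visit 6, also serves as the Early Termination visit. Sample Size Determination inflates the completer target "assuming an approximately 30% drop-out rate".

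Nothing in the synopsis or the schedule names a residual covariance structure, a degrees-of-freedom method, a robust standard error, or a fallback for non-convergence.

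**The concern.** With week as a factor, a random subject intercept plus independent residuals of one variance is a compound-symmetry model. Every visit gets the same variance and every pair of visits the same correlation, whether the visits are 7 days apart (Days 8 and 15) or 28 days apart (Days 8 and 36).

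The primary contrast is at Week 5 alone. Under compound symmetry its standard error uses a variance pooled over all four visits. If the Week 5 variance differs from that pooled value, the standard error is wrong even with complete data. If some Week 5 values are missing, a correlation that decays with time also distorts it. At stake are the primary p-value and the coverage of the primary confidence interval.

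**Working it through.** **The plan's own figures first.** Inputs from Sample Size Determination: effect size 0.46, two-sided 0.05, 90% power, 100 completers and 145 randomised per arm, about 30% dropout. n = 2(1.96 + 1.282)²/0.46² = 99.3, so 100 per arm. Power at 100 per arm is 90.2% (normal) or 89.9% (t). 100/(1 − 0.30) = 143, against 145 stated. The sample size reproduces and is not in dispute.

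**Assumed inputs.** The documents give no visit SDs or correlations, so all of these are assumptions.
- r = Week 1 SD / Week 5 SD, with SD_w = r + (1 − r)(w − 1)/4 at w = 1, 2, 3, 5, so that the Week 5 SD is 1.
- Correlation: constant (0.4, 0.6, 0.8); decaying, ρ^(weeks apart) with ρ = 0.7, 0.8, 0.9; or mixed, s + (1 − s)ρ^(weeks apart), with s = 0.3 and ρ = 0.8, or s = 0.5 and ρ = 0.7, 0.8, 0.9.
- Dropout completely at random. For 30% missing at Week 5, the last-visit probabilities are 0.1, 0.1, 0.1, 0.7.

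**Complete data.** Ratio of model SE to true SE = √(mean of SD_w²)/SD_5, and type I error = 2[1 − Φ(1.96 × ratio)].
- r = 1.0: ratio 1, error 5.0%.
- r = 0.9: SDs 0.9, 0.925, 0.95, 1. Mean variance (0.8100 + 0.8556 + 0.9025 + 1)/4 = 0.8920, ratio 0.944, error 6.4%.
- r = 1.1: SDs 1.1, 1.075, 1.05, 1. Mean variance (1.2100 + 1.1556 + 1.1025 + 1)/4 = 1.1170, ratio 1.057, error 3.8%.

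**With missing data.** Find the compound-symmetry variance and correlation to which the likelihood fit converges under the assumed true covariance. Then take ratio = √(model-based variance / sandwich variance) for the Week 5 mean, and use the same error formula. At ρ = 0.8 per week and 30% missing, the ratio is 1.006, 0.952 and 0.898 for r = 1.1, 1.0 and 0.9. At constant correlation 0.6 it is 1.063, 1.000 and 0.938.

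| r | No missing data | 30% missing, constant correlation | 30% missing, decaying correlation |
|---|---|---|---|
| 1.1 (SDs fall) | 3.8% | 3.7% | 4.6–4.9% |
| 1.0 (equal) | 5.0% | 5.0% | 5.9–6.2% |
| 0.9 (SDs rise) | 6.4% | 6.6–6.7% | 7.6–7.8% |

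At equal SDs, mixed correlation gives 5.5–6.0%. Earlier or later dropout moves the results by about 0.2 points at most. If only 10% are missing at Week 5 (an illustrative value), equal SDs give about 5.0–5.3%.

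**Simulation with the Baseline covariate.** 145 per arm, 30% missing, common Baseline slope −0.3, 10,000 replicates, Monte Carlo SE 0.2–0.3 points. At ρ = 0.8 per week, compound symmetry rejects a true null 5.8% of the time at r = 1.0 and 8.0% at r = 0.9. At constant correlation 0.6 and r = 1.0 it rejects 5.2%. An unstructured covariance rejects 4.5–5.3% in all six settings run, which extended over r = 0.7 to 1.2.

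**The case against.** **A fuller section may settle it.** The available text is the synopsis and schedule. Inclusion criterion 14 refers to a medications section that lies outside it, so a longer body exists, and a synopsis often leaves out covariance detail. This stands as a limit: what can be shown is that the synopsis does not state the structure, not that the whole plan omits it.

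**The MMRM label points elsewhere.** The label often goes with an unstructured residual covariance, and a subject effect does not exclude one. A reader might infer that the sponsor has committed to compound symmetry. The documents do not support that, because they never say the residuals are independent with one variance. But the label names no structure either, and the one within-subject term that is written down is a random effect. Either way the covariance behind the primary test is not fixed by this text, and the same rewording settles both readings.

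**The 30% may overstate missing Week 5 data.** CMAI is scheduled at Early Termination, so many who withdraw may contribute a late value. How those values are assigned to weeks is not stated. If they count as Week 5, missingness falls and so does the part of the distortion that comes from dropout. The part that comes from unequal SDs remains.

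**The size is assumed.** This stands in full. With equal SDs the effect is modest, and with complete data or constant correlation it is nil.

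**Conclusion.** The point holds in conditional form. Fitted as written, the primary model gives a valid Week 5 test and interval only if visit variances are equal and, where data are missing, correlations are constant.

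With equal SDs the type I error is 5.0–6.2% at 30% missing and about 5.0–5.3% at 10% missing. A 10% SD difference between Week 1 and Week 5 moves it to about 6.4–7.8% if SDs rise, or 3.7–4.9% if they fall. Interval coverage is the complement: about 92.2% (100 − 7.8) to 96.3% (100 − 3.7) across those two 10% cases.

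A reader might infer that the trial's false-positive rate is heavily inflated, for example to 8–12%. Rates in that range generally need the Week 1 SD to be 20–30% below the Week 5 SD. No passage supports such a change, and the direction reverses if SDs shrink. The figures show sensitivity, not an expected error rate. They also assume dropout completely at random; dropout that depends on earlier scores was not examined. The change is worth making because the remedy costs almost nothing and protects the primary test in either direction.

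**What to change.** Before unblinding, replace the random subject effect in the model sentence with an unstructured within-subject covariance across Weeks 1, 2, 3 and 5, with no separate random intercept. State the degrees-of-freedom method, for example Kenward-Roger. At this sample size it matters little: the critical values used in the simulation were 1.972 and 1.96. Prespecify a simpler structure with a sandwich standard error in case the unstructured fit does not converge. A fallback that indexes correlation by visit order would treat the 7-day gap from Week 1 to 2 like the 14-day gap from Week 3 to 5, so the sandwich standard error should be part of the rule. If a fuller statistical section already says this, bring the synopsis into line with it.

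Cost: wording only. The covariance goes from 2 parameters to 10 (4 variances and 6 covariances). If 145 per arm still holds for the two continuing arms, 2 × 145 = 290 subjects support that easily; the available text does not give the final size after amendment 2 stopped randomisation to bupropion. There is a small chance of non-convergence, which the fallback covers. At equal SDs, nominal power falls by at most about 0.8 points against compound symmetry, and that apparent gain comes from a standard error that is too small.
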